Appendix A: COPD Exacerbation (primary outcome), All-cause mortality (secondary outcome)

COPD Exacerbation

Measured 1 day after drug initiation in primary diagnosis position specified below and inpatient care setting -

COPD (Inpatient, Primary)

ICD-9 Diagnosis: 491.x, 492.x, 496 ICD-10 Diagnosis: J41.x, J42, J43.x, J44.x

OR

Measured 1 day after drug initiation in any diagnosis position specified below and inpatient and outpatient care setting AND steroid use within 14 days -

COPD (Any care setting, Any position)

ICD-9 Diagnosis: 491.x, 492.x, 496 ICD-10 Diagnosis: J41.x, J42, J43.x, J44.x

AND

Corticosteroid systemic administration and/or oral prescription of --

- Prednisone
- Prednisolone
- Methylprednisolone
- Dexamethasone
- Hydrocortisone

All-Cause Mortality

Identified using the discharge status codes-

Optum-Inpatient/Outpatient

- 20 = EXPIRED
- 21 = EXPIRED TO BE DEFINED AT STATE LEVEL
- 22 = EXPIRED TO BE DEFINED AT STATE LEVEL
- 23 = EXPIRED TO BE DEFINED AT STATE LEVEL
- 24 = EXPIRED TO BE DEFINED AT STATE LEVEL

- 25 = EXPIRED TO BE DEFINED AT STATE LEVEL
- 26 = EXPIRED TO BE DEFINED AT STATE LEVEL
- 27 = EXPIRED TO BE DEFINED AT STATE LEVEL
- 28 = EXPIRED TO BE DEFINED AT STATE LEVEL
- 29 = EXPIRED TO BE DEFINED AT STATE LEVEL
- 40 = EXPIRED AT HOME (HOSPICE)
- 41 = EXPIRED IN A MEDICAL FACILITY (HOSPICE)
- 42 = EXPIRED PLACE UNKNOWN (HOSPICE)

Marketscan-Inpatient

- 20 Died
- 22 Died
- 23 Died
- 24 Died
- 25 Died
- 26 Died
- 27 Died
- 28 Died
- 29 Died
- 40 Other died status or Expired at home (Hospice claims only) (depends on year)
- 41 Other died status or Expired in medical facility (Hospice claims only) (depends on year)
- 42 Other died status or Expired place unknown (Hospice claims only) (depends on year)
- 21 Died or Disch./Transf. to court/law enforcement (depends on year)

#	INSPIRE trial definitions	Implementation in routine care	References/Rationale	Color coding
			Please see the following Google drive for further details or any missing information_ https://drive.google.com/drive/fold ers/1WD618wrywYjEaXzfLTcuK-	
	Trial details - Intended S with label change - 2 weeks run-in		VCcnb6b-gV	Criteria
	EXPOSURE vs. COMPARISON			Adequate mapping in claims
	Tiotropium 18 mcg once daily vs. Salmeterol/fluticasone propionate (SFC) 50/500 mcg twice daily	SFC vs. Tiotropium		Intermediate mapping in
	Aim: To evaluate the effect of tiotropium compared to SFC on healthcare utilization of COPD exacerbations	Exposure: SFC Reference: Tiotropium		claims
	PRIMARY OUTCOME			Poor mapping or cannot be measured in claims
		Measured 1 day after drug initiation in primary diagnosis position and inpatient care setting		
	Primary endpoint: Healthcare utilization COPD exacerbation rate	COPD (Inpatient, Primary) ICD-9 Diagnosis: 491.x, 492.x, 496 ICD-10 Diagnosis: J41.x, J42, J43.x, J44.x OR Measured 1 day after drug initiation in any diagnosis position any care setting AND steriod use within 14 days COPD (Any care setting, Any position) ICD-9 Diagnosis: 491.x, 492.x, 496 ICD-10 Diagnosis: J41.x, J42, J43.x, J44.x AND Corticosteriod systemic administration and/or oral prescription of: - Prednisone - Prednisolone - Methylprednisolone - Dexamethasone - Hydrocortisone		Can't be measured in claims but not important for the analysis
	Tiotropium 18 mcg once daily vs. SFC 50/500 r			
	· · · · · · · · · · · · · · · · · · ·	Age 40 to 80 years old at the time of drug initiation		
2	Smoking history of ≥ 10 pack years			
3a	Diagnosis of COPD	Measured from the start of all available data to and including the day of drug initiation in any diagnosis position and in the inpatient and outpatient care setting COPD ICD-9 Diagnosis: 491.x, 492.x, 496 ICD-10 Diagnosis: J41.x, J42, J43.x, J44.x		

3b	Clinical history of at least 1 COPD exacerbation	Measured since all available data to 43 days prior to drug initiation in primary diagnosis position and inpatient care setting COPD (Inpatient, Primary) ICD-9 Diagnosis: 491x, 492.x, 496.0 ICD-10 Diagnosis: J41, J42.x, J43.x, J44.x OR Measured since all available data to 43 days prior to drug initiation in any diagnosis position, inpatient and outpatient care setting AND steriod use within 30 days COPD ICD-9 Diagnosis: 491.x, 492.x, 496.0 ICD-10 Diagnosis: J41.x, J42, J43.x, J44.x AND Corticosteriod systemic administration and/or prescription - Prednisone - Prednisolone - Methylprednisolone - Methylprednisolone - Dexamethasone
4	Post bronchodilator FEV1 of < 50% of predicted normal	- Hydrocortisone
5	FEV1 / FVC ratio <70%	
6	Reversibility to 400 mcg albuterol of less or equal to 10% of predicted FEV1 at Visit 1	
7	A score of 2 or more on the Modified Medical Research Council dyspnea scale	
8	Free from exacerbation in the 6 weeks prior to screening	Included in the exclusion criteria
	EXCLUSION CRITERIA	
1	COPD exacerbation in the 6 weeks prior to screening	Measured 42 days prior to and including the day of drug initiation in prescription claims COPD (Inpatient, Any) ICD-9 Diagnosis: 491.x, 492.x, 496.0 ICD-10 Diagnosis: J41.x, J42, J43.x, J44.x OR COPD (Any care setting, Any position) ICD-9 Diagnosis: 491.x, 492.x, 496.0 ICD-10 Diagnosis: J41.x, J42, J43.x, J44.x AND Corticosteriod systemic administration and/or prescription - Prednisone - Prednisolone - Methylprednisolone - Dexamethasone - Hydrocortisone

[figure not shown]
		7
		Measured 180 days prior to and including the day of drug initiation in any diagnosis position in the inpatient and outpatient care setting
		A 11 /0 P: 111: 400 L 3
		Asthma (3 Diagnosis within 180 days)
		ICD-9 Diagnosis: 493.x
		ICD-10 Diagnosis: J45.x
		Eczema
		ICD-9 Diagnosis: 692.x
2	Current asthma, eczema, atopic dermatitis and/or allergic rhinitis	ICD-10 Diagnosis: L23.x, L24.x
	Current astrima, eczema, atopic dermatitis and/or anergic minitis	
		Atopic dermatitis
		ICD-9 Diagnosis: 691.x
		ICD-10 Diagnosis: L20.x
		To Diagnosis. E20.X
		Allowed
		Allergic rhinitis
I		ICD-9 Diagnosis: 477.x
		ICD10 Diagnosis: J30.x
—		Measured since all available data to and including the day of drug initiation in any diagnosis
		position in the inpatient and outpatient care setting
		position in the imputions and outputions care setting
I		Dulmanary Fibracia ay Interstitial Lung Disease (U.S.)
I		Pulmonary Fibrosis or Interstitial Lung Disease (ILD)
		ICD-9 Diagnosis: 515, 516.3x, 516.8, 516.9
I		ICD-10 Diagnosis: J84.10, J84.111, J84.112, J84.113, J84.114, J84.115, J84.116, J84.117, J84.09,
		J84.2, J84.89, J84.9
		L
		Sarcoidosis
		ICD-9 diagnosis: 135
		ICD-10 diagnosis: D86.0, D86.2
3	Has a known respiratory disorder other than COPD (e.g. lung cancer, sarcoidosis, tuberculosis or lung fibrosis)	Lymphangioleiomyomatosis
ľ	Thas a known respiratory disorder other than corp (e.g. rung cancer, sarcoldosis, tuberculosis or rung runosis)	ICD-9 diagnosis: 516.4
		ICD-10 diagnosis: J84.81
		Primary/Pulmonary Tuberculosis
		ICD-9 diagnosis: 010.x, 011.x
		ICD-10 diagnosis: A15.x
		Cystic Fibrosis
I		ICD-9 Diagnosis: 277.0x
		ICD-10 Diagnosis: E84.xx
I		Pulmonary Hypertension/Other Pulmonary Heart Disease
		ICD-9 Diagnosis: 416 vy
		Measured 180 days prior to and including the day of drug initiation in any diagnosis position in the inpatient and outpatient care setting
		Narrow-angle Glaucoma
I		
		ICD-9 Diagnosis: 365.02, 36s.06, 365.2x
		ICD-10 Diagnosis: H40.03x, H40.2xx,
		Prostatic hyperplasia or obstruction of the neck of the bladder
I	Ulas paranu anala glaupama mastatia humanalasia ar abstruction of the mak of the hadder that in the continue of the	
4	Has narrow-angle glaucoma, prostatic hyperplasia or obstruction of the neck of the bladder that in the opinion of the	ICD-9 Diagnosis: 600.x
	investigator should prevent the subject from entering the study	ICD-10 Diagnosis: N40.x
		OR
		[
		At least one 30-day supply presciption claims for oral:
		Alfuzosin, doxazosin, tamsulosin, silodosin, finasteride 5 mg, dutasteride
ь		

[figure not shown]
_		Measured since all available data to and including the day of drug initiation in any diagnosis
		position in the inpatient and outpatient care setting
		Lung transplant
		ICD-9 Diagnosis: V42.6, 996.84
		ICD-10 Diagnosis: Z94.2, T86.810, T86.811, T86.819
		ICD-9 Procedure: 33.5x ICD-10 Procedure: OBYMOZO, OBYMOZ1, OBYMOZ2, OBYKOZO, OBYKOZ1, OBYKOZ2, OBYLOZO,
		OBYLOZ1, OBYLOZ2
5	Has undergone lung transplantation and/or lung volume reduction	CPT-4 Code: 32850 - 32856
		Lung volume reduction surgery (LVRS) ICD-9 Procedure: 32.22, 32.3x
		ICD-10 Procedure: 0BBC0ZZ, 0BBC4ZZ, 0BBD0ZZ, 0BBD4ZZ, 0BBF0ZZ, 0BBF4ZZ, 0BBG0ZZ,
		OBBG4ZZ, OBBH0ZZ, OBBH4ZZ, OBBJ0ZZ, OBBJ4ZZ, OBBK0ZZ, OBBK4ZZ, OBBL0ZZ, OBBL4ZZ,
		OBBMOZZ, OBBM4ZZ
		CPT/HCPCS codes: 32491, 32672, G0302, G0303, G0304, G0305
6	Female who is a nursing mother	
		Measured since all available data to and including the day of drug initiation in any diagnosis
		position in the inpatient and outpatient care setting
		LTOT
7	Requires regular (daily) long-term oxygen therapy (LTOT)	ICD-9 Diagnosis: V46.2
		ICD-10 Diagnosis: Z99.81
		CPT/HCPCS code: E0424, E0441, E0443
		Measured 180 days prior to and including the day of drug initiation with prescription for oral:
		Acebutolol, Atenolol, Betaxolol, Bisoprolol, Carteolol, Carvedilol, Labetalol, Metoprolol,
8	Is receiving beta-blockers (except eye drops)	Metiranolol, Nebivolol, Nadolol, Propranolol, Pindolol, Sotalol, Penbutolol, Oxprenolol
9	Has a serious, uncontrolled disease likely to interfere with the study	
10	Has received any other investigational drugs within the 4 weeks prior to Visit 1	
		Measured 180 days prior to and including the day of drug initiation in any diagnosis position in
		the inpatient and outpatient care setting
		Alcohol Abuse or Dependence
		ICD-9 diagnosis: 291.xx, 303.xx, 305.0x, 571.0x, 571.1x, 571.2x, 571.3x, 357.5x, 425.5x, E860.0x,
		V11.3x
11	Has, in the opinion of the investigator, evidence of alcohol, drug or solvent abuse	ICD-10 diagnosis: F10.x, K70.x, G62.1, I42.6, 099.31x
		Drug Abuse or Dependence
		ICD-9 diagnosis: 292.xx, 304.xx, 305.2x-305.9x, 648.3x ICD-10 diagnosis: F11.x, F12.x, F13.x, F14.x, F15.x, F16.x, F17.2x, F18.x, F19.x, F55.2, G62.0,
		099.32x
		U99.32X
		099.52X
12	Has a known or suspected hypersensitivity to beta2-agonists, inhaled corticosteroids, anticholinergic agents or any components of the formulations (e.g. lactose or milk protein)	U99.32X

		Measured 180 days prior to and including the day of drug initiation in prescription claims
13	Exclude use of Salmeterol, tiotropium, and fluticasone containing inhaler use within 180 days prior to CED	Brand names - STIOLTO RESPIMAT SEREVENT SEREVENT DISKUS ARNUITY ELLIPTA BREO ELLIPTA TRELEGY ELLIPTA FLOVENT HFA FLOVENT DISKUS ARMONAIR RESPICLICK ARMONAIR
		OR Generic name -
		TIOTROPIUM BROMIDE/OLODATEROL HCL SALMETEROL XINAFOATE

Optum MarketScan

[figure not shown]
BEFORE PS MATCHING

[figure not shown]

The c-statistics for the propensity score model, pre-matching was 0.689. The post-matching c-statistic was 0.523.

The c-statistics for the propensity score model, pre-matching was 0.7. The post-matching c-statistic was 0.516.

UNMATCHED

UNIVIATCHED		ODTUM			MADVETCCAN			POOLED			
		OPTUM			MARKETSCAN			POOLED			
	Referent - Tiotropium	Exposure - Salmeterol/Fluticasone	St. Diff	Referent - Tiotropium	Exposure - Salmeterol/Fluticasone	St. Diff	Referent - Tiotropium	Exposure - Salmeterol/Fluticasone	St. Diff		
Number of patients	21,689	30,570	St. DITT	36,727	64,653	St. DITT	58,416	95,223	St. DITT		
Calendar Time - Year of Initiation (2004 - 2020)	21,089	30,370		30,727	64,633		38,416	95,225			
2004-2006; n (%)	1,330 (6.1%)	3,505 (11.5%)	-0.1915	5,640 (15.4%)	15,357 (23.8%)	-0.2128	6,970 (11.9%)	18,862 (19.8%)	-0.218		
2007-2008; n (%)	2,190 (10.1%)	3,669 (12.0%)	-0.0606	5,594 (15.2%)	11,223 (17.4%)	-0.0596	7,784 (13.3%)	14,892 (15.6%)	-0.065		
2009-2011; n (%)	4,060 (18.7%)	6,299 (20.6%)	-0.0478	9,988 (27.2%)	17,461 (27.0%)	0.0045	14,048 (24.0%)	23,760 (25.0%)	-0.023		
2012-2015; n (%)	6,704 (30.9%)	8,124 (26.6%)	0.0951	11,489 (31.3%)	15,233 (23.6%)	0.1732	18,193 (31.1%)	23,357 (24.5%)	0.148		
2016-2018; n (%)	5,091 (23.5%)	6,116 (20.0%)	0.0849	4,016 (10.9%)	5,379 (8.3%)	0.0883	9,107 (15.6%)	11,495 (12.1%)	0.101		
2019-Mar. 2020; n (%)	2,314 (10.7%)	2,857 (9.3%)	0.0467	4,010 (10.570)	5,575 (6.576)		2,314 (10.7%)	2,857 (9.3%)	0.047		
200											
DMG-Age	67.67 (10.33)	64.58 (13.34)	0.2590	65.73 (11.22)	62.49 (14.22)	0.2530	66.45 (10.90)	63.16 (13.94)	0.263		
mean (sd)		66.00 [56.00, 74.00]	0.2590	65.73 (11.22)	62.49 (14.22)	0.2530	65.49 (10.90)	63.28 (13.94)	0.263		
median [IQR] DMG - Gender	68.00 [60.00, 75.00]	66.00 [56.00, 74.00]	0.1070	64.00 [58.00, 74.00]	62.00 [54.00, 73.00]	0.1502	65.49 (10.90)	63.28 (13.94)	0.177		
Male; n (%)	7,779 (35.9%)	10,307 (33.7%)	0.0462	14,471 (39.4%)	22,933 (35.5%)	0.0806	22,250 (38.1%)	33,240 (34.9%)	0.067		
Female: n (%)	13,910 (64.1%)	20,263 (66.3%)	-0.0462	22.256 (60.6%)	41.720 (64.5%)	-0.0806	36,166 (61.9%)	61,983 (65.1%)	-0.067		
DMG - Geographic region	13,510 (04.1%)	20,203 (00.3%)	0.0402	22,230 (00.0%)	41,720 (04.3%)	0.0000	30,100 (01.5%)	01,363 (03.176)	0.007		
Northeast; n (%)	2,144 (9.9%)	2,997 (9.8%)	0.0034	5,662 (15.4%)	10,090 (15.6%)	-0.0055	7,806 (13.4%)	13,087 (13.7%)	-0.009		
South; n (%)	9,881 (45.6%)	13,979 (45.7%)	-0.0020	13,969 (38.0%)	23,938 (37.0%)	0.0207	23,850 (40.8%)	37,917 (39.8%)	0.020		
North Central; n (%)	4.602 (21.2%)	6.546 (21.4%)	-0.0049	12,524 (34,1%)	21.068 (32.6%)	0.0318	17,126 (29.3%)	27,614 (29.0%)	0.007		
West; n (%)	5,062 (23.3%)	7,048 (23.1%)	0.0047	4,572 (12.4%)	9,557 (14.8%)	-0.0701	9,634 (16.5%)	16,605 (17.4%)	-0.024		
DRS - Combined comorbidity score, 180 days	, , , , , , , , , , , , , , , , , , , ,	, , , , , , , , , , , , , , , , , , , ,		· · · · ·	, , , , , ,			 			
mean (sd)	1.43 (1.73)	1.20 (1.67)	0.1353	1.13 (1.45)	0.94 (1.39)	0.1338	1.24 (1.56)	1.02 (1.49)	0.144		
median [IQR]	1.00 [0.00, 2.00]	1.00 [0.00, 2.00]	0.0000	1.00 [0.00, 2.00]	1.00 [0.00, 1.00]	0.0000	1.00 (1.56)	1.00 (1.49)	0.000		
DRS - Frailty Score: Empirical Version (mean)											
mean (sd)	0.18 (0.06)	0.17 (0.06)	0.1667	0.17 (0.05)	0.16 (0.05)	0.2000	0.17 (0.05)	0.16 (0.05)	0.200		
median [IQR]	0.17 [0.14, 0.21]	0.16 [0.13, 0.20]	0.1667	0.16 [0.13, 0.19]	0.15 [0.12, 0.18]	0.2000	0.16 (0.05)	0.15 (0.05)	0.200		
PLM - Smoking ; n (%)	6,731 (31.0%)	5,954 (19.5%)	0.2671	6,588 (17.9%)	6,674 (10.3%)	0.2197	13,319 (22.8%)	12,628 (13.3%)	0.249		
PLM-Pneumonia; n (%)	1,409 (6.5%)	1,750 (5.7%)	0.0334	2,786 (7.6%)	4,561 (7.1%)	0.0192	4,195 (7.2%)	6,311 (6.6%)	0.024		
PLM - Oxygen usage; n (%)	1,538 (7.1%)	1,440 (4.7%)	0.1020	3.158 (8.6%)	3.635 (5.6%)	0.1170	4,696 (8.0%)	5,075 (5.3%)	0.109		

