6.3.1 Outcome variables

Effectiveness outcome variables of interest (definitions provided in **Appendix A**):

- Primary outcome: Healthcare utilization exacerbation rate per year (although the trial definition include 1) COPD hospitalizations or 2) exacerbations that required corticosteroids and/or antibiotics, in our emulation, we focused on 1) hospitalizations with COPD in the primary diagnosis position or 2) exacerbations that required corticosteroids. We did not include antibiotic use as part of the outcome definition because of our inability to determine whether the antibiotics were being used for COPD or some other indication)
- Secondary outcome:
 - All-cause death

Control outcomes of interest (control outcomes only serve to assess aspects of study validity but are not further interpreted): Pneumonia

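### The secondary outcome named all-cause death counts only deaths carried by discharge status codes, and its MarketScan list includes a code that means a live transfer in some years

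*Combined protocol and SAP*

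**What the plan says.** Section 6.3.1 lists "All-cause death" as the secondary outcome. Appendix A gives its operational definition, "Identified using the discharge status codes", and then one code list per database.

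- **Optum.** The list is headed "Optum-Inpatient/Outpatient". It holds codes 20 to 29 and 40 to 42. Code 21 appears as "21 = EXPIRED TO BE DEFINED AT STATE LEVEL", with no year qualifier.
- **MarketScan.** The list is headed "Marketscan-Inpatient". It holds the same code numbers, but code 21 is labelled "21 Died or Disch./Transf. to court/law enforcement (depends on year". No rule says which years count.

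Both lists include hospice codes 40 to 42, which cover deaths at home and in an unknown place. No death index, enrolment-file death date or other source is named, and no under-capture caveat accompanies the outcome. Section 6.3.2 also makes death one of the events that end as-treated follow-up, without saying which codes define it there.

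**The concern.** The name promises every death, whereas the definition delivers deaths that produced a coded claim in the listed settings. Someone who dies without a hospital or hospice claim would leave follow-up under another heading, plausibly end of enrolment or end of index exposure. For the primary outcome, Section 6.3.1 explains openly where the emulation departs from the trial (antibiotic-only exacerbations are left out). Mortality gets no such note, so a reader would take the label literally.

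Two consequences follow. First, a ratio of recorded deaths equals the ratio of deaths only if the two arms have the same chance that a death is recorded. Capture depends on facility or hospice contact, and COPD hospitalisation is itself part of the primary outcome, so equal capture should be stated as an assumption. Second, a code that means a live transfer in some years adds events that are not deaths. If these fall equally in both arms, they pull the ratio towards 1.

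**Working it through.** **1. Reproducing the plan's figures.** The only death figures are in the censoring table of Section 9. Appendix B gives 18,017 + 31,122 = 49,139 matched patients per arm, 98,278 in all.

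- Total: 368 + 338 = 706; 706 / 98,278 = 0.72%.
- Tiotropium: 368 / 49,139 = 0.75%.
- SFC: 338 / 49,139 = 0.69%.

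All three match. The non-zero censoring rows sum to 706 + 8,037 + 63,915 + 2,286 + 11,722 + 11,612 = 98,278. These are as-treated censoring counts from the balance run with the dummy outcome, with median follow-up of 88 days in Optum and 113 in MarketScan (Section 9). They are not the mortality result.

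**2. Share of patients in the narrower source.** MarketScan: 2 × 31,122 = 62,244; 62,244 / 98,278 = 63.3%.

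**3. Under-capture.** The documents do not give the share of deaths outside the listed settings. If a share m is missed, missed deaths = 706 × m / (1 − m). Under an assumed m of 30% to 60%:

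- m = 0.30: 706 × 0.30 / 0.70 = 303.
- m = 0.60: 706 × 0.60 / 0.40 = 1,059.

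If m is the same in both arms, this costs precision and leaves the ratio about where it was. If capture differs:

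observed ratio = true ratio × (capture in SFC / capture in tiotropium).

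The crude count ratio is 338 / 368 = 0.918 (equal arm sizes, not adjusted for follow-up). Its log standard error is √(1/368 + 1/338) = 0.075. A hypothetical capture of 55% against 50% gives a factor of 55 / 50 = 1.10. Depending on which arm has the better capture, an observed 0.918 would then correspond to 0.918 / 1.10 = 0.835 or 0.918 × 1.10 = 1.010. Since ln(1.10) = 0.095, the shift is about 1.3 standard errors. With no capture gap, the factor is 1.

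**4. Code 21.** The documents give neither the number of code 21 records nor the years with the live-transfer meaning, so no corrected count can be computed. MarketScan cohort entry runs from 2004 to 2018 (Section 5.2.1), so a year rule has many data years to cover. For scale only, suppose that a share f of referent-arm events is false, that the same number occurs in the other arm, and that the true ratio is 0.85 (the value that the plan uses for the primary outcome):

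observed ratio = (1 − f) × 0.85 + f.

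- f = 1%: 0.8515.
- f = 5%: 0.8575.

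**5. Possible reach into the primary analysis.** If the same codes define the death censoring event, a live MarketScan patient with code 21 would be censored wrongly. The ceiling in the balance run is all 706 recorded deaths, 0.72% of patients. The code 21 part can only be smaller.

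**The case against.** The strongest reply is that the definition is disclosed code by code, that death is a secondary outcome with no power calculation or success criterion, and that replication is aimed at the exacerbation rate. That is fair, and it limits the weight of the point. It does not make the label accurate or supply the missing year rule.

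Several stronger readings are tempting, and the documents do not support them.

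- **That the outcome is mostly in-hospital death, or that home deaths are missed outright.** Codes 40 to 42 pick up some hospice deaths at home or in an unknown place, and Optum also uses outpatient claims. No breakdown by place of death is given.
- **That the difference between databases biases the drug comparison.** Matching is 1:1 within each database (18,017 per arm in Optum, 31,122 per arm in MarketScan), so different capture between databases does not by itself favour an arm. Different capture between arms would.
- **That a gap between arms is likely.** Nothing shows one. After matching, earlier hospitalisation is 11.5% against 11.4% (Appendix B), and the trial's exacerbation rate ratio was 0.967 (Section 1.5).
- **That a pooled mortality estimate is planned.** Primary-outcome risk, power and baseline tables are pooled; for mortality the plan does not say.
- **That code 21 corrupts as-treated censoring.** Section 6.3.2 does not tie its death event to the Appendix A codes.

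It can also be said that the year note on code 21 may reflect a rule applied in the programming. Possibly so, but none is written, and the list as it stands treats the code as a death.

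**Conclusion.** The point holds as a wrong label and an incomplete coding rule for the secondary outcome. Both databases count only deaths with a qualifying discharge status on a claim, and the setting is narrower in the database that supplies 63% of matched patients. MarketScan code 21, as written, counts some live discharges as deaths.

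The size of neither error can be derived from the documents. The code 21 error is probably small. The figures of 303 to 1,059 missed deaths and a 10% shift in the ratio rest on assumed capture shares and show scale only. Bias in the ratio requires capture to differ between arms, in which case it could go either way. Any effect on the as-treated primary analysis depends on the same codes being used for censoring, which is not stated, and it would touch fewer than 0.72% of patients in the balance run.

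**What to change.** - Count MarketScan code 21 only in data years when it denotes death, and write those years into Appendix A; otherwise drop the code. Dropping it would lose true deaths in the years when it does mean death.
- Rename the outcome in Section 6.3.1 and Appendix A as death recorded by discharge status (facility/hospice claims).
- Report it by database before any pooling, and say whether it will be pooled. Section 9 and Appendix B already report by database.
- State as a limitation that deaths without such a claim are missed, and that the ratio could be biased if capture differs by arm.
- State in Section 6.3.2 which codes define death as a censoring event.

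Identical care settings should not be forced by discarding Optum outpatient deaths, because that would remove real events.

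The cost is some wording and one year condition in the code; no linkage or new data are needed. The downside is a narrower claim for the secondary outcome.

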PLM - Moderate COPD exacerbation - [Count with 30 days to CED]*	0.00 [0.00, 0.93]	0.00 [0.00, 0.93]	0.0000	0.00 [0.00, 0.73]	0.00 [0.00, 0.73]	0.0000	0.00 (1.04)	0.00 (1.55)	0.000
mean (sd)	0.02 (0.10)	0.01(0.09)	0.1051	0.01 (0.08)	0.01 (0.08)	0.0000	0.01 (0.09)	0.01 (0.08)	0.000
median [IQR]	0.00 [0.00, 0.00]	0.00 [0.00, 0.00]	0.0000	0.00 [0.00, 0.00]	0.00 [0.00, 0.00]	0.0000	0.00 (0.09)	0.00 (0.08)	0.000
PLM - Moderate exacerbations >=1 in 365 days before CED; n (%)	12,493 (69.3%)	12,555 (69.7%)	-0.0087	19,559 (62.8%)	19,638 (63.1%)	-0.0062	32,052 (65.2%)	32,193 (65.5%)	-0.006
PLM - Moderate exacerbations >= 2 in 365 days before CED; n (%)	7,747 (43.0%)	7,755 (43.0%)	0.0000	11,085 (35.6%)	11,239 (36.1%)	-0.0104	18,832 (38.3%)	18,994 (38.7%)	-0.008
PLM - Severe COPD exacerbation - [Count with 365 to 181 days before CED] *									
mean (sd)	0.03 (0.18)	0.03 (0.18)	0.0000	0.05 (0.21)	0.05 (0.21)	0.0000	0.04 (0.20)	0.04 (0.20)	0.000
median [IQR] PLM - Severe COPD exacerbation - [Count with 180 to 31 days before CED] *	0.00 [0.00, 0.00]	0.00 [0.00, 0.00]	0.0000	0.00 [0.00, 0.00]	0.00 [0.00, 0.00]	0.0000	0.00 (0.20)	0.00 (0.20)	0.000
PLM - Severe COPD exacerbation - [Count with 180 to 31 days before CED] *mean (sd)	0.02 (0.14)	0.02 (0.13)	0.0000	0.03 (0.15)	0.03 (0.15)	0.0000	0.03 (0.15)	0.03 (0.14)	0.000
median (Su)	0.02 (0.14)	0.00 [0.00, 0.00]	0.0000	0.00 [0.00, 0.00]	0.00 [0.00, 0.00]	0.0000	0.00 (0.15)	0.00 (0.14)	0.000
PLM - Severe COPD exacerbation - [Count with 30 days lookback] *	0.00 [0.00, 0.00]	0.00 [0.00, 0.00]	0.0000	0.00 [0.00, 0.00]	0.00 [0.00, 0.00]	3.0000	0.00 (0.13)	0.00 (0.1-1)	+ 0.000
mean (sd)	0.00 (0.01)	0.00 (0.01)	0.0000	0.00 (0.01)	0.00 (0.01)	0.0000	0.00 (0.01)	0.00 (0.01)	0.000
median [IQR]	0.00 [0.00, 0.00]	0.00 [0.00, 0.00]	0.0000	0.00 [0.00, 0.00]	0.00 [0.00, 0.00]	0.0000	0.00 (0.01)	0.00 (0.01)	0.000
PLM - Severe exacerbations >=1 in 365 days before CED; n (%)	1,038 (5.8%)	1,015 (5.6%)	0.0086	2,595 (8.3%)	2,650 (8.5%)	-0.0072	3,633 (7.4%)	3,665 (7.5%)	-0.004
PLM - Severe exacerbations >=2 in 365 days before CED ; n (%)	93 (0.5%)	86 (0.5%)	0.0000	198 (0.6%)	198 (0.6%)	0.0000	291 (0.6%)	284 (0.6%)	0.000
PLM - GOLD C/D Status ; n (%)	5,385 (29.9%)	5,395 (29.9%)	0.0000	9,771 (31.4%)	9,873 (31.7%)	-0.0065	15,156 (30.8%)	15,268 (31.1%)	-0.006
PRX - LABA only ; n (%)	93 (0.5%)	99 (0.5%)	0.0000	348 (1.1%)	332 (1.1%)	0.0000	441 (0.9%)	431 (0.9%)	0.000

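### Appendix A lists ICD-9 496 for the COPD diagnosis and the outcome but 496.0 for exacerbation history and the six-week exclusion, so as written a 496-coded exacerbation counts after index but not before it

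*Combined protocol and SAP*

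**What the plan says.** In Appendix A the inpatient arm of the primary outcome reads "COPD (Inpatient, Primary) ICD-9 Diagnosis: 491.x, 492.x, 496 ICD-10 Diagnosis: J41.x, J42, J43.x, J44.x", and the steroid arm uses the same codes. Inclusion 3a, the COPD diagnosis, reads "COPD ICD-9 Diagnosis: 491.x, 492.x, 496 ICD-10 Diagnosis: J41.x, J42, J43.x, J44.x".

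The two exacerbation criteria at entry read differently. The inpatient arm of Inclusion 3b is "COPD (Inpatient, Primary) ICD-9 Diagnosis: 491x, 492.x, 496.0 ICD-10 Diagnosis: J41, J42.x, J43.x, J44.x" and its steroid arm is "COPD ICD-9 Diagnosis: 491.x, 492.x, 496.0 ICD-10 Diagnosis: J41.x, J42, J43.x, J44.x". The inpatient arm of Exclusion 1 is "COPD (Inpatient, Any) ICD-9 Diagnosis: 491.x, 492.x, 496.0 ICD-10 Diagnosis: J41.x, J42, J43.x, J44.x", and its steroid arm again gives 496.0.

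Section 6.3.2 starts follow-up the day after initiation. Section 2 says the implementation history is kept in the platform. The Appendix A table refers to an external folder for further detail, which is not part of the document.

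**The concern.** Inclusion 3b and Exclusion 1 are the only claims-based stand-ins for two of the trial's requirements: a history of exacerbation, and six exacerbation-free weeks before entry. If their code list is narrower than the outcome's, two errors follow. Patients whose only qualifying history was coded 496 are dropped by 3b. Patients with a recent exacerbation coded 496 pass Exclusion 1, and a continuing episode could be counted as an outcome from the first day of follow-up. Median follow-up is only 88 days in Optum and 113 in MarketScan (Section 9), so early events carry weight.

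**Working it through.** **Lists side by side (Appendix A).**

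| Definition | Code in question | Other notation |
|---|---|---|
| Outcome, inpatient arm | 496 | 491.x; J41.x; J42 |
| Outcome, steroid arm | 496 | 491.x; J41.x; J42 |
| Inclusion 3a | 496 | 491.x; J41.x; J42 |
| Inclusion 3b, inpatient arm | 496.0 | 491x; J41; J42.x |
| Inclusion 3b, steroid arm | 496.0 | 491.x; J41.x; J42 |
| Exclusion 1, inpatient arm | 496.0 | 491.x; J41.x; J42 |
| Exclusion 1, steroid arm | 496.0 | 491.x; J41.x; J42 |

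The split is consistent: 496.0 stands in all four exacerbation-entry lists and nowhere in 3a or the outcome. The lists also differ in diagnosis position and steroid window, but that is a separate matter.

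**String check.** A claim coded 496 does not equal 496.0 and does not begin with it. With the point removed, 496.0 becomes 4960, which is not 496 either.

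**One claim traced through the rules.** Take a visit coded 496 only, with prednisone (the days are illustrative):
- day +10: meets the outcome;
- day −10: does not meet Exclusion 1;
- day −100: does not meet 3b;
- any day up to index: does meet 3a.

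A record that also carries 491.x or 492.x counts in every place. ICD-10 records are not touched by the 496 question.

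**Flowchart rows that depend on these lists (Section 5.3).** They reproduce:
- 3b, Optum: 246,632 − 110,352 = 136,280. MarketScan: 353,500 − 153,003 = 200,497.
- Exclusion 1, Optum: 136,280 − 33,666 = 102,614. MarketScan: 200,497 − 34,019 = 166,478.
- Removed by the two together, Optum: 110,352 + 33,666 = 144,018. MarketScan: 153,003 + 34,019 = 187,022.

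**Share of entries in years when the ICD-9 list would apply (Appendix B, matched, pooled).** The document gives no changeover date, so the range is an assumption.
- If ICD-9 applied through 2011: (6,615 + 7,233 + 12,123 + 6,511 + 7,344 + 12,201) / 98,278 = 52,027 / 98,278 = 52.9%.
- If through 2015: (52,027 + 14,449 + 14,326) / 98,278 = 80,802 / 98,278 = 82.2%.

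This is the share of index dates in those years, not the share of patients affected. No counts by code are given, so the latter cannot be derived. Inclusion 3b looks back over all available data, so later entrants may also rest on ICD-9 history.

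**The case against.** The strongest reply is that this is a typing slip. The inpatient arm of 3b also has 491x, J41 and J42.x, so loose notation is present in the same cell, and the programmed list may well have used 496. That is plausible and nothing in the document refutes it. Nothing confirms it either, and these are the operative definitions.

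A second reply uses Table 1 (unmatched). Moderate exacerbation counts average 0.52 to 0.95 over days 180 to 31, which is 0.10 to 0.19 per 30 days (multiplying by 30/150). In the 30 days to entry the means are 0.01 to 0.02, a fall of about 89% to 94%, or 86% to 90% if the means that print as 0.01 or 0.02 sit at the top of their rounding. So Exclusion 1 as run removed most recent exacerbations as that covariate counts them. This stands, but it speaks to code 496 only if the covariate includes 496, and its code list is not given.

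In the other direction, a reader might infer a leak of known size from the non-zero row "PLM - Moderate COPD exacerbation - [Count with 30 days to CED", by treating the squared SD as a proportion of patients. The figures do not allow it. A non-negative whole-number count with mean m has variance at least m(1 − m). A mean printed as 0.02 is at least 0.015, so the SD would be at least √(0.015 × 0.985) = 0.12, yet matched Optum tiotropium shows 0.10. A related count has a median of 0.28. These are not plain 0/1 counts. Moreover, under the same list and rule as Exclusion 1, a 30-day count inside a 42-day exclusion would be zero. A non-zero value therefore shows some difference in definition, not specifically a missed 496.

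**Conclusion.** The inconsistency is in the text and is complete: three lists with 496, four with 496.0, and no statement of equivalence. The finding does not depend on whether 496.0 is a valid code. If the two mean the same, the notation needs aligning; if they do not, entry and outcome use different definitions of the same event. The statement is limited to the exacerbation criteria, since 3a does accept 496 at entry. How many patients are affected, and in which arm, cannot be computed.

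Two further inferences are tempting and are not supported:

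- **That the databases show missed claims.** Exclusion 1 removed 33,666 / 136,280 = 24.7% in Optum and 34,019 / 200,497 = 17.0% in MarketScan, the source with more early entries. But 3b uses the same 496.0 and should then have dropped more in MarketScan. It dropped slightly fewer: 153,003 / 353,500 = 43.3% against 110,352 / 246,632 = 44.7%. Background frequency explains most of the Exclusion 1 gap: the MarketScan-to-Optum ratio of the 180-to-31-day means is 0.68 / 0.95 = 0.72 for tiotropium and 0.52 / 0.72 = 0.72 for SFC, against 17.0 / 24.7 = 0.69.
- **That the leak favours one arm.** Systemic steroid use in the 30 days to entry is 11.9% for SFC and 6.3% for tiotropium before matching. It is in the propensity score model, and after matching it is 6.6% and 6.9%.

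The point is therefore a definition to correct and an implementation to verify, not a demonstrated bias.

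**What to change.** Replace 496.0 with 496 in both arms of Inclusion 3b and both arms of Exclusion 1. In the inpatient arm of 3b only, change 491x, J41 and J42.x to 491.x, J41.x and J42. Entry and outcome then share one COPD code list.

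Confirm from the archived platform implementation which list was run, and record the answer. If 496 was run, the correction is editorial. If 496.0 was run literally, re-run 3b, Exclusion 1, the flowchart and the propensity score match, and repeat the balance and power tables, before any outcome analysis. The review stop at the end of Section 10 is the natural place for this.

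It would also help to state the code list and rule behind the 30-day moderate-exacerbation covariate, so that its non-zero values can be understood. The cost is a lookup and a text edit, and in the worse case a repeat of cohort assembly and matching with a changed cohort size.
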